4.3. Withdrawal of Subjects

A subject may withdraw from the study at any time for any reason without prejudice to their future medical care by the physician or at the institution. The Investigator or Sponsor may withdraw the subject at any time (eg, in the interest of subject safety). The withdrawal of a subject from investigational product by the Investigator should be discussed where possible with the Medical Monitor before the subject stops investigational product.

If a subject is withdrawn from the study, every effort will be made by the Investigator to complete and report the reasons for withdrawal as thoroughly as possible. The reason for termination must be clearly documented on the appropriate page of the electronic case report form (eCRF). Study withdrawal should include the final assessments, as required by the protocol and every effort should be made to perform the End-of-study procedures (see Table 2).

A termination eCRF must be completed for all enrolled subjects.

Subjects who discontinue will not be replaced.

Subject Stopping Criteria

If an adverse event (AE) is a reason for discontinuation, then "Adverse event" must be recorded as the reason for discontinuation on the eCRF.

Reasons for discontinuation include but are not limited to:

- Adverse event (including, but not limited to, symptomatic pericardial effusion or cardiac tamponade)
- Intercurrent event preventing the administration of tesevatinib for more than 28 days
- Protocol violation
- Request by a regulatory agency (eg, institutional review board [IRB])
- Withdrawal by subject
- Lost to follow-up
- Lack of efficacy
- Pregnancy
- Other (must be specified).

Subjects 'Lost to Follow-up' Prior to Last Scheduled Visit

At least 3 documented attempts must be made to contact any subject lost to follow-up at any time point prior to the last scheduled contact (office visit or telephone contact). One of these

documented attempts must include a written communication sent to the subject's last known address via courier or mail (with an acknowledgement of receipt request) asking that they return any unused investigational product and return to the site for final safety evaluations.

5. CONCOMITANT MEDICATION

5.1. Concomitant Medication and Potential Interactions

Subjects should not receive additional therapeutic treatment during the study period without the approval of the Sponsor's Medical Monitor.

If the subject must use a concomitant medication during the study, it is the responsibility of the Principal Investigator to ensure that details regarding the medication are recorded on the eCRF.

Subjects should avoid ingesting grapefruit and grapefruit juice with study drug or at any time during the study. Subjects are not permitted to take concomitant medications that inhibit (eg, ketoconazole, itraconazole, erythromycin, clarithromycin) or induce (eg, dexamethasone, phenytoin, carbamazepine, rifampicin, or phenobarbital) the CYP3A4 isozyme (see Appendix 1). Additionally, subjects should not take medications that are associated with a risk of QTcF interval prolongation and/or torsades de pointes (see Appendix 2).

Tesevatinib is highly protein bound, and other drugs that are also highly protein bound with the exception of warfarin (eg, diazepam, furosemide, dicloxacillin, propranolol, and phenytoin) should be avoided.

Based on in vitro evaluation, tesevatinib may be a weak substrate for P-glycoprotein (P-gp). Since P-gp is extensively expressed in multiple tissues and is involved in the transport of a vast variety of biological molecules, drugs such as colchicine, verapamil, tamoxifen, cyclosporine, and digoxin should be monitored.

Anti-emetics and antidiarrheal medications should not be administered prophylactically before initial treatment with study drug. At the discretion of the Investigator, treatment of symptoms with anti-emetic and antidiarrheal medications may be undertaken per standard clinical practice.

Since tesevatinib is a potent inhibitor of multidrug and toxic compound extrusion (MATE) transporter proteins, increased levels of concomitant medications that are secreted by the kidney proximal tubule cells into the renal tubule by MATE transporter proteins may occur. Thus, subjects taking cephalexin, cimetidine, dofetilide, fexofenadine, metformin, procainamide, and pyrimethamine should be monitored carefully.

5.2. Management of Subjects Requiring Concomitant Medications Associated with QT Interval Prolongation

Tesevatinib has been associated with prolongation of the QT interval. Subjects requiring treatment with drugs known to be associated with torsades de pointes or significant QT interval prolongation may not be enrolled into this study. This includes Class IA anti-arrhythmics (eg, quinidine, procainamide); Class III anti-arrhythmics (eg, amiodarone, sotalol, dofetilide); phenothiazine anti-psychotics: (eg, chlorpromazine, mesoridazine, pimozide, thioridazine); quinolone antibiotics (eg, gatifloxacin, moxifloxacin, sparfloxacin);

macrolide antibiotics (eg, erythromycin, clarithromycin, and troleandomycin) and other drugs that have a contraindication or boxed warning regarding QT prolongation in the prescribing information. A list of concomitant medications associated with a risk of QTc interval prolongation and/or torsades de pointes can be found in Appendix 2.

Drugs associated with QT interval prolongation should be avoided in subjects receiving study drug. Should a subject develop a condition for which a medication known to affect QT interval is indicated, consideration should be given to the additive risk of QT interval prolongation versus the potential benefit of treatment with the required medication and/or study drug. Contact the Medical Monitor prior to the administration of the concomitant medication.

Beginning at Month 2, subjects who require short-term (2 to 3 weeks, not to exceed 21 days) treatment with a concomitant medication associated with QT interval prolongation should have the study drug held until the concomitant treatment course is complete. The decision on whether the subject can continue on study following this interruption will be determined by the Medical Monitor. If the subject restarts study drug after discussion with the Medical Monitor, an ECG will be performed prior to restarting study drug.

6. INVESTIGATIONAL PRODUCT

6.1. Identity of Investigational Product

Tesevatinib will be provided in 50 mg tablets; matched placebo will also be provided.

Tesevatinib tablets are white to off-white round tablets that contain 50% (w/w) active product ingredient in the current lactose-based immediate-release formulation.

6.2. Administration of Investigational Product(s)

Interactive Voice/Web Response System for Investigational Product Management

Study drug assignment and administration will use an interactive voice/web response system (IVRS/IWRS). Details are provided in Section 7.4.

Dosing

Subjects will be provided with an adequate supply of study drug and instructions for taking the study drug at home. Unused drug must be returned to the study site at each visit for accounting and reconciliation.

Study drug may be taken with or without food at approximately the same time every morning. Subjects should drink a full glass of water (approximately 8 ounces [240 mL]) immediately after study drug administration. Grapefruit and similar (pomelo fruit, Seville orange, etc.) products should be avoided for the duration of study treatment. On days when subjects report to the study site for study procedures, study drug dosing will be done at the study site.

Subjects must be instructed not to make up missed doses unless the missed dose can be taken within 12 hours of the normal dosing time. Subjects should not re-take study drug doses in the event of vomiting.

Subjects will receive study drug for 28 days after the initiation of treatment. After the initial 28-day safety and tolerability assessment period, subjects will, at the Investigator's discretion, continue to receive study drug for a total of 24 months from the initiation of treatment or until the development of unacceptable toxicity, noncompliance, or withdrawal of consent by the subject, or investigator decision.

Blinding the Treatment Assignment

This is a double-blind, placebo-controlled study.

Allocation of Subjects to Treatment

This is a randomized, double-blind, placebo-controlled study. The actual treatment given to individual subjects is determined by a randomization schedule.

Subject screening numbers are assigned to all subjects as they consent to take part in the study. Within each site (numbered uniquely within a protocol), this number is assigned to subjects according to the sequence of presentation for study participation.

A randomization number/unique identifier is allocated once eligibility has been determined. Once a randomization number/unique identifier has been assigned, that number must not be used again if, for example, a subject is withdrawn from the study. If a randomization number/unique identifier is allocated incorrectly the Clinical Research Associate (CRA)/Study Monitor must be notified as soon as the error is discovered.

Individual subject treatment is automatically assigned by the IVRS/IWRS.

Unblinding the Treatment Assignment

Data that may potentially unblind the treatment assignment (ie, investigational product serum concentrations, treatment allocation, and investigational product preparation/accountability data) will be handled with special care during the data cleaning and review process. Any data that may unblind study team personnel will be presented as blinded information or otherwise will not be made available. If applicable, unblinded data may be made available to quality assurance representatives for the purposes of conducting independent drug audits.

The treatment assignment must not be broken during the study except in emergency situations where the identification of the investigational product is required for further treatment of the subject. In the event that the treatment assignment is broken, the date, the signature of the person who broke the code, and the reason for breaking the code are recorded on the IVRS/IWRS and the source documents. Upon breaking the blind, the subject is withdrawn from the study, but should be followed up for safety purposes. Any code-breaks that occur must be reported to the Sponsor. Code-break information is held by the pharmacist/designated person at the site and by Medical Monitor for the study or designee.

6.3. Labeling, Packaging, Storage, and Handling

Labeling

The following information will be printed on the label for clinical lots of study drug:

KD019 or Placebo 50 mg Tablets – 32 count

Lot: xxxxx.xxx

Direction: Take as directed by physician.

Store at controlled room temperature of 20°-25°C (66°-77°F). Brief excursions permitted

between 15°C and 30°C (59°F and 86°F).

Caution: Federal law prohibits the transfer of this drug to any person other than the patient for whom it was prescribed.

Caution: New Drug – Limited by Federal Law to Investigational Use 21CFR312.6 (a).

Keep out of the reach of children and pets.

Kadmon Corporation, LLC New York, NY 10016 USA

Packaging

Tesevatinib 50 mg tablets and matched placebo tablets are packaged in 30-cc high-density polyethylene bottles capped with 28-mm, childproof caps.

Changes to Sponsor-supplied packaging prior to dosing may not occur without full agreement in advance by the Sponsor.

Storage

The Investigator has overall responsibility for ensuring that investigational product is stored in a secure, limited-access location. Limited responsibility may be delegated to the pharmacy or member of the study team, but this delegation must be documented.

Study drug must be stored at a controlled room temperature of 20°-25°C (66°-77°F). Brief excursions are permitted between 15°C and 30°C (59°F and 86°F). The Sponsor must be notified upon discovery of any excursion from the established range. Temperature excursions will require site investigation as to cause and remediation. The Sponsor will determine the ultimate impact of excursions on the investigational product and will provide supportive documentation as necessary.

Under no circumstances should product be dispensed to subjects until the impact is determined and product is deemed appropriate for use by Sponsor.

Study drug must be inventoried according to applicable regulations.

6.4. Investigational Product Quality Complaints

Once a Product Quality Complaint is identified, investigators must report it to Kadmon. This includes any instances wherein the quality or performance of a Kadmon investigational product does not meet expectations (eg, inadequate or faulty closure, product contamination), the product does not meet the specifications defined in the application for the product (eg,

wrong product such that the label and contents are different products), or the product does not meet appearance specifications (eg, broken or chipped tablets).

6.5. Drug Accountability

Investigators will be provided with sufficient amounts of the investigational product to carry out this protocol for the agreed number of subjects. The Investigator or designee will acknowledge receipt of the investigational product documenting shipment content and condition. Accurate records of all investigational product dispensed, used, returned, and/or destroyed must be maintained as detailed further in this section.

The Investigator has overall responsibility for administering/dispensing investigational product. Where permissible, tasks may be delegated to a qualified designee (eg, a pharmacist) who is adequately trained in the protocol and who works under the direct supervision of the Investigator. This delegation must be documented in the applicable study delegation of authority form.

Dispensing records will document quantities received from Kadmon and quantities dispensed to subjects, including lot number, date dispensed, subject identification number, subject initials, and the initials of the person dispensing study drug. Reasons for deviation from the expected dispensing regimen also must be recorded.

The Investigator or his/her designee (as documented by the Investigator in the applicable study delegation of authority form) will administer/dispense the investigational product only to subjects included in this study following the procedures set out in the study protocol. Each subject will be given only the investigational product carrying his/her treatment assignment. All dispensing will be documented on the eCRFs and/or other investigational product record. The Investigator is responsible for assuring the retrieval of all investigational product from subjects. No investigational product stock may be removed from the site where originally shipped without prior knowledge and consent by the Sponsor. If such transfer is authorized by the Sponsor, all applicable local, state, and national laws must be adhered to for the transfer.

The Sponsor or its representatives must be permitted access to review the supplies storage and distribution procedures and records provided that the blind of the study is not compromised.

At study initiation, the study monitor will evaluate and obtain a copy of each site's written standard operating procedure for study drug disposal/destruction in order to ensure that it complies with the Sponsor's requirements.

With the written agreement of the Sponsor, at the end of the study all unused stock, subject returned investigational product, and empty/used investigational product packaging may be destroyed at the site or a local facility. In this case, destruction records identifying what was destroyed, when and how must be obtained with copies provided to the Sponsor. If the site cannot meet the Sponsor requirements for disposal, arrangements will be made between the site and the Sponsor or its representative for destruction or return of unused study drug supplies. Investigational products being returned to the Sponsor's-designated contractors must be counted and verified by clinical site personnel and the Sponsor (or designated contractor). For unused supplies where the original supplied tamper-evident feature is verified as intact,

the tamper evident feature must not be broken and the labeled amount is to be documented in lieu of counting. All certificates of delivery/drug receipts should be signed by the site representative to confirm contents of shipment. Shipment return forms, when used, must be signed prior to shipment from the site. Validated electronic return systems (ie, IVRS/IWRS) do not require a shipment form. Returned investigational products must be packed in a tamper-evident manner to ensure product integrity. Authorization from the Sponsor should be sought prior to any shipment of investigational products. Shipment or destruction of investigational products must be in accordance with local, state, and national laws.

Based on entries in the site drug accountability forms, it must be possible to reconcile investigational products delivered with those used and returned. All investigational products must be accounted for and all discrepancies investigated and documented to the Sponsor's satisfaction.

6.6. Subject Compliance

Subjects must be instructed to bring their unused investigational product and empty/used investigational product packaging to every visit. Drug accountability must be assessed at the container/packaging level for unused investigational product that is contained within the original tamper evident sealed container (eg, bottles, trays, vials) or at the individual count level for opened containers/packaging. The pharmacist/nominated person will record details on the drug accountability form.

In addition, subject diaries will be used to evaluate compliance. Subject diaries will be dispensed on Day 1 and reviewed at each visit.

6.7. Warnings, Precautions, and Management

Adverse events that have been associated with tesevatinib include the following: diarrhea, skin rash, QTcF prolongation, hepatotoxicity, and pulmonary toxicity. Study drug may be held for up to 28 days at the discretion of the Investigator (unless otherwise specified below), except during the first 28 days of dosing (Early Treatment Period).

Diarrhea

Diarrhea should be managed according to accepted practice (eg, with loperamide). Subjects with severe diarrhea who are unresponsive to loperamide or who become dehydrated may require interruption of study drug until resolution to ≤ mild in intensity. If subjects are in the monthly treatment period, drug may be held for up to 28 days. If severe diarrhea occurs during the 28-day Early Treatment Period, subjects must be discontinued from the study. In the event of severe or persistent diarrhea, nausea, anorexia, or vomiting associated with dehydration, study drug should be discontinued, and appropriate measures should be taken to rehydrate the subject intensively via intravenous administrations. Subjects should be advised to contact the investigator immediately if they develop significant diarrhea; should this occur, an electrolyte panel, including magnesium and potassium, and ECG should be performed.

Skin Rash

Skin rash should be managed according to locally accepted clinical recommendations. Study drug may be held up to 28 days at the discretion of the investigator and after discussion with the Medical Monitor. The following guidelines may be considered.

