1.3. Study Rationale

Rationale for the ADPKD Indication

In nonclinical studies, tesevatinib selectively inhibited key kinases and validated targets in animal models of PKD. Results from nonclinical efficacy studies demonstrated that tesevatinib possesses significant potential to prevent the formation of cysts due to an increased proliferation of renal ductal epithelial cells. Nonclinical studies using 2 rodent models (BPK mouse and PCK rat) of PKD have demonstrated that tesevatinib reaches its target, the kidneys, and inhibits the signaling pathway for MEK/ERK by inhibiting the phosphorylation of EGFR (and Src, Erb2, VEGFR2/KDR). The decreased phosphorylation of EGFR and Erb2 contributes towards decreased proliferation of epithelial cells in the kidneys and reduces renal enlargement in these 2 disease models.

In summary, both the nonclinical and clinical results to date suggest that tesevatinib may be a promising therapeutic for ADPKD.

Rationale for Dosage Selection

Safety reviews after the first 2 cohorts in Study KD019-101 (50 mg QD and 100 mg QD) deemed these cohorts to have adequate safety and to be tolerable. In the 150 mg QD cohort, 3 of 5 subjects enrolled withdrew consent primarily due to concerns with rash. It was noted that all 5 subjects in this cohort experienced rash within the first 28 days of treatment. In comparison, 4 out of 9 subjects in the 50 mg cohort and 1 out of 8 subjects in the 100 mg cohort experienced rash within the first 28 days. While rash at the 150 mg dose level did not meet strict safety criteria for defining the MTD, this dose level was considered intolerable for long-term administration in this population. Therefore, the MTD for daily dosing was determined to be 100 mg QD. While the MTD dose of 100 mg QD was based on criteria defined in the protocol, the occurrence of moderate QT prolongation in 2 subjects dosed at that level led to a decision later in the study to recommend 50 mg QD as the best tolerated daily dose.

Study KD019-101 is currently enrolling additional subjects at the dose of 50 mg QD (SILK cohort) in order to increase the robustness of the safety data in subjects with ADPKD treated with tesevatinib.

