6.7.1.2. Response to QTcF Interval Prolongation

The following guidelines should be used in the management of QTcF prolongation. Subjects will have ECGs performed as outlined in Table 2. If the average QTcF interval (from 3 consecutive ECGs taken with an interval of at least 1-2 minutes within 30 minutes) increases to > 60 msec above the highest average predose value (average of Day 1 predose and screening values) or to the level of ≥ 480 msec according to local site analysis:

- Hold study drug until central read is confirmed.
- Check electrolytes, especially magnesium and potassium; correct abnormalities as clinically indicated.
- Manage as clinically indicated with cardiology consultation as needed.
- Contact the Medical Monitor to discuss additional monitoring.

If results are confirmed by the central reader, the subject may be removed from the study after discussion with the Medical Monitor. If the subject continues in the study, appropriate management and ECG follow-up should be discussed with the Medical Monitor.

Elevated Amylase

If subjects develop an elevated serum amylase during the study that is $> 2.0 \times ULN$, then additional evaluations should be performed. These should include evaluating serum lipase, amylase isoenzymes, and fasting triglycerides as well as obtaining history regarding symptoms of pancreatitis, symptoms of dry mouth, and use of alcohol. The subject should have a drug holiday for 28 days, with amylase measured at the end of the drug holiday. If the amylase is back to the baseline value after the end of the drug holiday, study drug may be restarted, and amylase measured approximately 14 days later, and then at the start of each cycle of study drug administration. If results continue to be abnormal, the subject will be removed from study. If an elevated serum amylase that is $> 2.0 \times ULN$ occurs a second time, the subject will be removed from the study.

Elevated Creatinine Phosphokinase

If subjects develop an elevated serum CPK during the study that is $> 2.0 \times$ ULN, additional evaluations should be performed. These should include evaluating serum CPK isoenzymes as well as obtaining history regarding muscle-related symptoms or strenuous or prolonged exercise.

Pulmonary Toxicity

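### Protocol Section 6.7 gives both a pause and a stop for severe diarrhea with dehydration after the first 28 days, and leaves unclear whether the early-period bar on holds covers rash

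*Protocol*

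**What the plan says.** All the management text is in Protocol Section 6.7.

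- **Lead paragraph.** The investigator may hold study drug for up to 28 days at discretion, subject to anything specified later in the section, "except during the first 28 days of dosing (Early Treatment Period").
- **Diarrhea, pause.** Subjects with severe diarrhea who do not respond to loperamide, or "who become dehydrated may require interruption of study drug until resolution" to mild or less. Then: "If subjects are in the monthly treatment period, drug may be held for up to 28 days".
- **Diarrhea, early period.** "If severe diarrhea occurs during the 28-day Early Treatment Period, subjects must be discontinued from the study".
- **Diarrhea, stop.** For severe or persistent diarrhea (also nausea, anorexia or vomiting) that is "associated with dehydration, study drug should be discontinued", with intensive intravenous rehydration. This sentence names no study period and does not mention restarting.
- **Skin Rash.** "Study drug may be held up to 28 days at the discretion of the investigator and after discussion with the Medical Monitor". The Early Treatment Period is not mentioned.

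Three other provisions give these rules statistical weight. The Efficacy Population (Protocol 9.5, SAP 3.3) requires 12 months of treatment and central MRI reads at baseline and after 12 months. It is the primary population for efficacy (SAP 3.9). Subjects who discontinue are not replaced (Protocol 4.3).

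**The concern.** The same clinical event, in the same period, has two prescribed actions. With about 25 to 30 sites applying the text themselves, the action may depend on which sentence an investigator relies on.

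This bears first on subject management, because a safety rule should give one answer. It also bears on the primary analysis. A pause can leave a subject able to complete 12 months of treatment; a permanent stop before Month 12 cannot. Section 1.2 describes diarrhea and rash as class effects of EGFR inhibitors, so any site-dependent stopping would be expected to fall mainly on the tesevatinib arm. The primary comparison would then lose subjects selectively from one arm, for reasons tied to treatment and partly to how a site read the protocol.

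The rash question matters because Section 6.7.1.1 places the typical onset in the first few weeks, which overlaps the period when the lead paragraph excludes discretionary holds.

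**Working it through.** The point rests on wording, so the first check is to apply the Diarrhea paragraph to each situation.

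| Situation | Pause sentence applies? | Stop sentence applies? | Result |
|---|---|---|---|
| Days 1–28, severe | No; the early-period sentence requires discontinuation from the study | Yes, if dehydrated | No pause either way; agrees with the lead paragraph |
| After Day 28, severe, unresponsive to loperamide, not dehydrated | Yes | No | Pause only |
| After Day 28, severe, dehydrated | Yes | Yes | **Conflict** |
| After Day 28, persistent but not severe, dehydrated | No | Yes | Stop only |

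The conflict is confined to the third row. The fourth row sharpens it: within this paragraph, the less severe event leads only to a stop, while the more severe one also has a pause available.

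**Does discontinued simply mean paused here?** The section's own usage says not. For pulmonary toxicity, drug is held during evaluation and discontinued if interstitial lung disease is diagnosed. Table 4 separates reintroduction of drug from its discontinuation.

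**Rash.** The lead paragraph's hold and the Skin Rash hold have the same length and the same discretionary basis. The rash sentence adds discussion with the Medical Monitor and omits the early-period exclusion. Two readings remain: the general exclusion still applies, or the rash sentence is a separate permission. The text does not choose between them.

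**Consequence for analysis.** A subject stopped early has an End-of-study MRI about 30 days after the last dose. Nothing further is scheduled, so a subject stopped well before Month 12 would usually have no Month 12 scan. SAP 3.10 repeats the endpoint analyses in the mITT population, but SAP 3.2.4 generally does not impute missing data, so that analysis recovers only part of the loss.

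**Scale, for context only.** The planned power reproduces. Inputs from Protocol 9.12 are a difference of 83.6 − 26.4 = 57.2 mL, SD 90.0 mL and two-sided alpha 0.05. With noncentrality 57.2 / [90 × √(1/n₁ + 1/n₂)] on n₁ + n₂ − 2 degrees of freedom, 40 per group gives 57.2 / (90 × 0.2236) = 2.84 and power of 80.2%, against the stated 80% or so.

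Holding placebo at 40 and assuming a smaller evaluable tesevatinib arm:

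| Tesevatinib evaluable (assumed) | Power |
|---|---|
| 40 | 80.2% |
| 38 | 79.1% |
| 35 | 77.3% |
| 32 | 75.3% |
| 30 | 73.7% |

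These rows show only what a given loss would cost. They do not predict the loss. They also describe a t-test on the raw change, whereas SAP 3.9.2 analyzes log₁₀ change by ANCOVA.

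**The case against.** **The diarrhea sentences can be read as escalation.** The pause sentence is permissive, and the later one adds intensive intravenous rehydration, so a reader could take it as the rule for worse cases. That is a sensible way to write such a rule, but the protocol does not say it. Both sentences are triggered by severe diarrhea with dehydration, and no further criterion separates them. The overlap stands, though it is narrow.

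**The early-period limit may be general.** Section 6.2 describes the first 28 days as a safety and tolerability assessment, Section 5.2 allows holds for QT-prolonging medication only from Month 2, and the diarrhea rule also bars an early pause. This favors applying the limit to rash. Silence in the rash paragraph is therefore an ambiguity and not a contradiction, which is why rash is the smaller point.

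**A reader might infer that every hold rule in Section 6.7 clashes with the early-period limit.** The documents do not support that. The lead sentence limits holds at the investigator's discretion. The QTcF instruction ("Hold study drug until central read is confirmed"), the amylase drug holiday, the pulmonary hold and the Table 5 holds are directed by the protocol.

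**A reader might infer that a subject with early rash must keep dosing.** Section 4.3 lets the investigator or sponsor withdraw a subject at any time in the interest of safety. Only the option of a pause is unclear.

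**Conclusion.** The concern holds for one event: severe diarrhea with dehydration after the Early Treatment Period has two incompatible actions in one paragraph. The rash wording is a lesser ambiguity. Both should be corrected, because the rule affects subject safety and helps decide who reaches the primary efficacy population.

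The number of subjects affected cannot be stated. It is tempting to build an estimate from the earlier study, where "4 out of 9 subjects in the 50 mg cohort" had rash within 28 days. That count is of rash of any severity. The same sentence in Section 1.3 reports 1 of 8 at 100 mg, and the two cohorts together give 5/17 = 29%. Table 4 lists no hold at any grade of rash. No figure in the documents says how many such subjects would need a pause, and none gives a rate of severe diarrhea.

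The power cost of a few extra losses would be modest. The greater risk is selective loss from one arm. That rests on two assumptions: that these events occur mainly on tesevatinib, and that sites would in fact read the sentences differently.

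**What to change.** In Section 6.7, reconcile the two diarrhea sentences so that each situation (study period, severity, dehydration) leads to one action, and say whether study drug may be restarted. Reconcile the Skin Rash hold sentence with the lead paragraph by stating whether the exclusion of the first 28 days applies to rash. The sponsor's clinical and safety staff must choose the rules; none is proposed here.

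The cost is a few sentences of protocol text, the IRB approval that Section 10.3 requires for amendments, and a note to sites. No visits, subjects or SAP changes are needed. If subjects have already been managed under the present text, the adverse event listings in SAP 3.13.1, which include action taken, can show whether the same event was handled differently across sites.
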